We propose reporting both the pilot and efficacy study using CONSORT guidelines. This will enable us to explore the relationship between those who are potentially eligible, those who consent and those who engage, using key demographic indicators, age, gender, ethnicity, socio-economic status. Significant differences in these key demographic indicators at each point will inform our qualitative research, where we will purposively sample those who do not consent and those who withdraw to explore the reasons why and understand the perceived acceptability of the intervention or control for these participants.

A key area to explore in terms of reach is whether all potential participants are being identified and referred to the scheme. In previous studies of diversionary schemes for substance misuse offences some critics have highlighted the disproportionate inclusion of white, middle class, males that are not necessarily representative of the target demographic. To explore this, we plan on working with public health colleagues with access to LPD data to use a comprehensive cohort approach to understand outcomes for those who are referred or not referred to the scheme. This approach will allow anonymised aggregate analysis of differences between the cohort referred or not referred but also anonymised aggregate analysis of outcomes for those not referred. This information will allow us to quantify any inherent biases associated with referral in terms of key demographics and to further explore these with our stakeholder interviews. This approach will enable us to understand how generalisable the study results are and whether changes need to be made to referral pathways or intervention delivery to make the population more inclusive.

Exploring responsiveness

An aspect of our qualitative work with key stakeholders involves examining participants' positive and negative experiences of the referral process and intervention, exploring how these perspectives concur with those who deliver the intervention, explore at what points

negative and positive experiences are at their greatest and what steps could be taken to ameliorate these experiences to improve the delivery and acceptability of the intervention.

Exploring Adaptation

The mechanism of change will be explored using a mediation model approach and incorporating motivation, self-efficacy, and expectancy at month 6, adjusted for baseline covariates. Allocated group will be included as an interaction term. Exploring factors that impact on the mechanism of change will be assessed using stepwise regression analysis to model the relationship between pre-randomisation factors and observed outcomes at 6 months, separately for the primary outcome and for percent days abstinent from substance use. Interaction terms with allocation arm will be included in the analysis, and a significance level of 0.1 will be used to determine which factors are included in the regression model. Pre-randomisation factors include gender, age, ethnicity, IMD decile, adverse childhood experiences, anxiety and depression and family cohesion.

In addition to quantitatively understanding the mechanism of action, the qualitative analysis will provide an opportunity to explore the perceptions of the intervention from the point of view of a variety of stakeholders. The analysis will allow us to explore what elements of the interventions are useful and what elements are unnecessary, issues around how the interventions are planned and implemented and the perceived barriers or facilitators of implementation in usual practice.

Through a detailed exploration of the key dimensions, we plan on stating our logic model at the start of the project, revising this during the pilot phase and revise this again at the end of the efficacy stage. The logic model will incorporate the qualitative research exploring stakeholder perceptions of acceptability and usefulness, hindrances and facilitators associated with the process and intervention but will also combine quantitative analysis exploring adherence, dosage, fidelity, and mediators associated with behaviour change. This mixed methods synthesis will enable us to understand what works, how it works, when it works and for whom it works and provide a detailed elaboration of the mechanisms and processes through which it works.

Exploring factors affecting implementation

Within the CJS system there is no central recording mechanism for recording informal out of court disposals and diversions. It is estimated that 40% of first-time youth entrants to CJS receive an informal diversion. As part of the efficacy trial, we plan a survey of police forces in England to explore the nature and extent of diversion for first time substance use offences among young people, working in collaboration with colleagues with the police and senior staff involved in criminal justice at Public Health England. This survey would address the varieties of diversionary schemes employed, eligibility, referral mechanisms, numbers referred

annually and source of funding. This will provide an overview of the current state of play, where interventions take place, the process of implementation and the associated costs and source of funding.

Key questions addressed by the qualitative component will both be informed by, and inform, elements of the quantitative analysis, they include:

- Do participants, providers and police perceive any external or logistical issues as impacting referral, intervention delivery, attrition, or study assessments?
- What are participants' positive and negative intervention experiences and how do these fit with providers' perceptions? At what points in the intervention are these most likely?
- What reasons do participants offer for their misuse and for their intervention responses?
- Can practices associated with the intervention be amended to increase its acceptability and impact?
- Do police perceive the intervention as impacting participants' offending?

To address these research questions in depth, the qualitative aspect of the work will involve the collection of narrative accounts from a range of individuals using semi-structured interviews. These will be collected from young people participating, and staff involved in the programme delivery and professionally associated with the young people. Professionals will be sampled purposefully from the different staff groups, and young people will also be purposefully sampled.

To explore beyond the realms of the research project itself, we will also conduct several qualitative focus groups with key stakeholders not involved in the study itself. These groups will comprise 6 to 8 individuals and will be repeated until data saturation is reached. This purposive sample will be guided by the findings of the survey of practice across the country and include areas of low/ high activity, capacity, and deprivation. These focus groups will explore views on organisational capacity, intervention delivery, eligibility, referral mechanisms, the optimum number of standardised measures required to monitor intervention delivery, minimum standards of experience for interventionists, delivery of training and ongoing supervision. These focus groups will allow us to develop a set of minimum standards, standard operating procedures for training and intervention delivery and a training and an intervention delivery manual.

In addition to these focus groups, we will individually interview purposefully selected children and young people from across the country who meet the same criteria as the intervention participants but who have not received any intervention. Again, the purposive sample will be guided by diversity criteria (i.e., areas of low/high deprivation, age, gender, social class, and ethnicity). Participants will be asked to provide views on how their substance misuse has been handled and what might aid them/have aided them in reducing it as well as any involvement in non-violent offences. As with all the qualitative research in this project, sample size will be determined according to data saturation rather than a priori.

Synthesis of these data sources will allow a detailed overview of the implementation and processes associated with successful delivery of the intervention and a firm basis to conduct a pragmatic trial of effectiveness if warranted from the results of the efficacy evaluation.

Table 4: IPE methods overview

IPE Question	Data collection methods	Participants/ data sources (type, number)	Data analysis methods	Research questions addressed	Implementation/ logic model relevance
Fidelity/ adherence/ differentiation/ quality	Participant survey, therapeutic alliance, BECCI checklist, session data	370 participant surveys and TASC-r, BECCI fidelity assessment	Regression analysis	Quantification of the role fidelity, and quality plays in the outcomes observed	Better quality interventions that involve better alliance and communication between young people and practitioners are associated with better outcomes.
Dosage	Session planned and attended, outcome data	370 participant surveys, process database	Complier Average Causal Effect analysis	Estimation of the role dosage plays on observed outcomes at variable thresholds	Greater frequency of intervention is associated with better outcomes
	Factors associated with non-compliance	370 participant surveys, process database	Latent Class Analysis	Explore factors associated with non-compliance	Create targeted opportunities to reduce non-compliance and maximise acceptability.
Reach	Comprehensive Cohort Approach	Data on all young people referred to the service compared with data for those who consented	Logistic regression model with consent as the dependent outcome	Explore whether the intervention was accessible to all those referred to the services	Identify any potential issues with accessibility.
	Qualitative interviews with service	10 semi-structured interviews	Transcribing and inductive analysis to allow themes to	Identify any populations that experienced	Identify issues with accessibility

	leads and key stakeholders		emerge naturally	limited accessibility and the potential reasons for this.	and how these may be addressed
Responsiveness	Qualitative interviews with participants	15 semi-structured interviews with participants and 10 semi-structured interviews with key stakeholders, purposive sampling to get variety by site, age and ethnicity	Inductive analysis	To explore acceptability of the referral and intervention process. To explore positive and negative experiences and when these occur.	To understand how the referral and delivery processes can be maximised.
Adaption	Quantitative analysis	370 participant surveys	Mediation analysis including allocated arm as an interaction erm	To explore factors at baseline that mediate the outcomes observed	To understand the mechanisms of change and provide information for refinement of the Theory of Change Model.
	Qualitative analysis	15 semi-structured interviews with participants and 10 semi-structured interviews with key stakeholders, purposive sampling to get variety by site, age and ethnicity	Inductive analysis	To explore participant and practitioner perspectives on how the intervention works and perceived barriers or facilitators to the intervention	To understand who the how the intervention works and who it works for in order to refine the theory of change.

Implementation	Qualitative analysis	15 semi-structured interviews with participants and 10 semi-structured interviews with key stakeholders, purposive sampling to get variety by site, age and ethnicity	Inductive synthesis	Synthesis of qualitative findings to explore positive and negative experiences and how changes can be made to maximise the impact of the intervention.	Identify potential modifications that can be made to maximise the impact of the intervention.
----------------	----------------------	---	---------------------	--	---

Cost data reporting and collecting

Costs associated with delivering the intervention will be derived using a micro-costing approach accounting for the actual local costs and resources used in delivering the intervention and associated training. This will include salaries, resources, facilities, overheads, and management costs. The cost perspective will be that of the intervention provider. We will include any costs associated with supervision and additional training and use the time horizon of the trial to estimate staff turnover. We aim to estimate the cost of delivering the intervention in real practice rather than the cost of delivering the intervention in the trial. The cost data will be provided as mean cost per participant with 95% confidence intervals.

Ethics and registration

Ethical approval was sought and provided by an independent ethics committee at the University of Kent (SRC0498). The pilot study registration (ISRCTN133967729) is being updated and extended to cover the efficacy trial.

Data protection

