1. To conduct a prospective RCT to evaluate the efficacy of the intervention versus a standardised control on non-violent offences in the 6 months after randomisation and the frequency of substance use and wellbeing.
2. To conduct a micro-costing exercise to provide estimates of the cost of delivering the intervention from the perspective of the intervention delivery organisation.
3. To develop a prognostic model exploring the baseline demographics, psychological and family factors that may impact observed outcomes and using the results to elaborate mechanisms of change and where appropriate revise the intervention logic model.
4. To assess the fidelity of intervention delivery and explore the role adherence, fidelity, therapeutic alliance, interventionist factors, baseline demographic and psychological factors play in the outcomes observed for the intervention group.
5. To conduct a latent class analysis to explore potential interactions between population subgroups, intervention received, and outcomes observed.
6. To explore generalisability and inclusivity using a comprehensive cohort approach.
7. To explore the participant, police, and intervention provider perspectives on the acceptability of the referral process and intervention delivery and to explore key facilitators and hindrances to successful scaling-up of the intervention.
8. If the intervention is found to be effective, to develop a protocol for the scaling up and wider scale delivery of the intervention.

Design

Table 1: Trial design

Trial design, including number of arms		Two-arm individually randomised efficacy trial
Unit of randomisation		Young person
Stratification variables (if applicable)		Age group (10-14 years; 15-17 years) Police Force (Kent, Wigan, Sefton, Cornwall)
Primary outcome	variable	All offences 6 months post-randomisation
	measure (instrument, scale, source)	Local Police Database
Secondary outcome(s)	variable(s)	Self-reported offences, emotional regulation, substance use frequency, psychological health and well-being, situational confidence, readiness to change, expectancies.
	measure(s) (instrument, scale, source)	Self-Report Delinquency Scale (SRDS), Strengths and Difficulties Questionnaire (SDQ), Timeline Follow-Back (TLFB28), Warwick-Edinburgh Mental Well-being Scale (WEMWBS), Short Situational Confidence Questionnaire (SCQ-8), Readiness to Change Ruler (RR), Substance Use Effect Expectancy Scale (SUE)

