We will assess adherence by recording attendance at each element of the intervention and the control. For those in the intervention group we will assess fidelity by randomly recording 20% of brief intervention sessions stratified by age group, interventionist and site and independently score these using the Behavioural Change Counselling Index (BECCI; (Lane, 2002)). We will ask participants in the intervention arm to complete the short revised therapeutic alliance scale for children after the second intervention session (TASC-r; (Shirk and Saiz, 1992)). There is emerging evidence that the perceptions of interventionists play a key role in the quality of intervention delivered, particularly in terms of their perceived role legitimacy and self-efficacy, both targets of training and ongoing supervision. In order to assess these perceptions, we will ask interventionists to complete the Drug and Drug Using Populations Perceptions Questionnaire (DDPPQ; (Connors et al., 2019)) just prior to training and again 6-months after being trained.

Analysis

In the overall analysis, data from the internal pilot and efficacy study will be combined and analysed blind to group allocation. The efficacy analysis will be conducted and presented in accordance with the CONSORT guidelines. The validity of randomisation will be explored by presenting measures of central tendency and estimates of precision for continuous variables,

and proportions for categorical variables broken down by allocation arm and stratification factors.

The primary outcome is the frequency of non-violent offences at 6-months post-randomisation, and this will be conducted as an analysis by treatment allocated (ITT) and will include all available data maintaining participants as members of their allocated group. Prior to analysis we will conduct a series of diagnostic tests and assess the underlying assumptions prior to choosing an appropriate and statistically rigorous regression model.

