In addition to this we will explore differentiation between intervention and control groups. Our experience with similar large multi-centre RCT’s of brief interventions (Newbury-Birch et al., 2014, Deluca et al., 2020, Coulton et al., 2008) would suggest this control would need to consist of a minimally acceptable intervention including the provision of information and sources of support delivered by someone not involved in delivering the intervention. To explore the question of differentiation we will extend our recording to a 20% random sample of control interactions, stratified by interventionist and site. We will use the same BECCI tool to score these interactions, with the expectation they would score low on behaviour change content. Differentiation between intervention and control will be explored using the levels of agreement approach developed by Bland and Altman (Bland and Altman, 1986) to graphically present the extent to which intervention and control differ on each of the key behavioural change domains and to quantify the magnitude of differentiation after adjusting for known covariates.

Exploring Dosage

We plan on conducting a secondary analysis using a Complier Average Causal Effects (CACE) model using an instrumental variable framework. The usual approach to explore the role adherence is to conduct a per protocol analysis, where only those who received the intervention and control as prescribed are included. This can result in dropping large numbers of participants from the analysis and introduce bias. CACE analysis allows us to avoid this bias

by weighting the ITT treatment effect by the dose of intervention or control treatment received, this provides an unbiased estimate of the role of dosage in the outcomes observed.

In addition to this we would want to explore whether certain factors are associated with non-compliance to identify potential clusters of participants who do not comply. We will conduct a latent class analysis (LCA) to identify potential clusters associated with non-compliance, this will enable an exploration of whether there are sub-groups of participants who are harder to reach than others and by augmenting this quantitative approach with targeted qualitative interviews with young people and interventionists, enable the wider research group to explore what adaptations may be necessary to increase accessibility and compliance.

Exploring Reach

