[name]; Intervention delivery Kent.

[name]; Intervention delivery Cornwall.

[name]; Intervention delivery Sefton.

[name]; Intervention delivery Lancashire.

Risks

Our experience of similar studies has enabled us to develop and pilot several risk mitigations strategies. We have identified the following key risks:

1. Lack of engagement by stakeholders. We plan on actively engaging with all stakeholders to ensure the importance of the project is recognised. We aim to visit all sites early on and plan on engaging with staff at all levels in the partner organisations (LOW).

2. Potential contamination. As a randomised controlled trial, the potential for contamination is low. The design of the standardised control group, delivered by staff not involved in delivering the intervention, will address any potential for contamination. All follow-ups will be conducted blind to baseline allocation (LOW).

3. Poor recruitment. We have extensive experience of working with marginalised populations. In addition to clear referral and recruitment strategies we will ensure recruitment is constantly monitored to identify emerging issues, reduce barriers to participation by using few inclusion criteria and minimising exclusion criteria, providing clear information, and ensuring participants are clear on what the trial entails. Our previous experience with a similar population recruited 80% of those participants considered potentially eligible, in our pilot study we recruited 80% of those eligible. (LOW).

4. Poor adherence to follow-up. As our primary outcome measure is not participant assessed this issue relates in the main to the collection of secondary and process measures. In our previous studies with similar populations we have met, and exceeded, our target follow-up rate of 70% at 6-months and in our pilot study we followed up 88% across both groups. We have developed several follow-up strategies including multiple contact details, details of contactable others and ensuring participants are recompensed for the time spent engaging in follow-up assessments (LOW).

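### The Bland-Altman agreement approach needs paired scores, but intervention and control recordings are unpaired: name an unpaired adjusted comparison and reconcile it with Table 4

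*Protocol*

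**What the plan says.** The protocol section on fidelity/adherence, differentiation and quality (Implementation and process evaluation) sets out how the plan will check that the two arms delivered different content. For the control arm, "we will extend our recording to a 20% random sample of control interactions, stratified by interventionist and site". The same BECCI tool is applied to both arms, and control contacts are expected to score low. The section then states: "Differentiation between intervention and control will be explored using the levels of agreement approach developed by Bland and Altman". It gives the approach two aims. One is a graphical display of how the arms differ, domain by domain. The other is "to quantify the magnitude of differentiation after adjusting for known covariates".

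The intervention recordings are described under Compliance in the protocol as "randomly recording 20% of brief intervention sessions stratified by age group, interventionist and site". Table 1 of the protocol gives the design as "Two-arm individually randomised efficacy trial". Risks, item 2, says that the control is "delivered by staff not involved in delivering the intervention", and the differentiation section makes the same point.

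Two other places bear on this. Table 4 of the protocol (IPE methods overview) has one row for fidelity, adherence, differentiation and quality, and gives regression analysis as its method. The SAP contains no differentiation analysis.

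**The concern.** Limits of agreement are the mean of the within-pair differences plus or minus 1.96 times their standard deviation. They describe how closely two measurements of the same subject agree. The protocol asks something else: how far two independent groups of sessions differ in behaviour-change content. Without a unit measured under both conditions there is no within-pair difference to summarise, so the analyst would have to invent pairs or depart from the named method.

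At stake is how cleanly the trial can report the separation between its arms. The control is an active contact from the same provider organisation. If the primary result is null, the BECCI comparison is one of the pieces of evidence on whether the contrast between arms was weak. It should be reported as an estimate with an interval that has a clear meaning.

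**Working it through.** **1. Is there any unit that supplies pairs?**

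- Young person: no. The arms are parallel with individual randomisation (Protocol, Table 1), and the SAP's Compliance section says control participants cannot get the intervention.
- Deliverer: no. Control staff are separate from intervention staff (Protocol, differentiation section and Risks item 2).
- Session: no. There are two sessions in the intervention arm and one in the control arm (Protocol, Intervention). The recordings are separate 20% random samples, and no matching is described. Shared strata such as site do not create pairs.

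**2. How many recordings?** The documents give no count, so these follow from the 20% sampling and assume full attendance.

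- All 370 participants (185 per arm): intervention 0.20 × 185 × 2 = 74; control 0.20 × 185 × 1 = 37.
- The 294 efficacy-stage participants (147 per arm): intervention 0.20 × 147 × 2 = 58.8, about 59; control 0.20 × 147 = 29.4, about 29.

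One-to-one pairing leaves 74 − 37 = 37 of 74 intervention recordings unused, or 59 − 29 = 30 of 59. Either way that is about half.

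**3. What would the limits show?** For arbitrary pairs of independent scores with common standard deviation s, the within-pair difference has standard deviation s√2. The limits therefore lie about 1.96 × √2 × s either side of the mean difference. The documents give no BECCI standard deviation, so a range is assumed.

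- s = 0.5: 1.96 × 1.414 × 0.5 = 1.39 points.
- s = 1.0: 1.96 × 1.414 × 1.0 = 2.77 points.

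These half-widths depend on how much sessions vary, whatever the gap between the arms.

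**4. Do the limits depend on the pairing chosen?** One simulated data set was used, with 37 scores per arm, assumed standard deviation 0.6 and true difference 1.5. The same scores were re-paired at random 5,000 times.

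- Mean difference: 1.62 every time.
- Lower limit: between −0.15 and 0.79.
- Upper limit: between 2.45 and 3.39.
- Unpaired mean difference on the same scores: 1.62, 95% CI 1.39 to 1.85, with no pairing needed.

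**5. Precision of the mean difference, like for like** (s = 1.0, before any allowance for clustering; halve the figures for s = 0.5).

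- 37 arbitrary pairs: 1.96 × √(2/37) = ±0.46.
- Unpaired, 74 against 37: 1.96 × √(1/74 + 1/37) = ±0.39.
- Unpaired, 59 against 29: 1.96 × √(1/59 + 1/29) = ±0.44.

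For the mean difference itself, forced pairing therefore costs only modest precision.

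**6. Covariates and consistency.** Standard limits of agreement have no step that yields a covariate-adjusted difference between arms, yet the sentence promises one. A regression would yield it, and regression is what Table 4 lists.

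**The case against.** The centre line of a Bland-Altman plot is the mean difference. With equal numbers used per arm, it equals the difference in arm means however the sessions are paired. A reader might infer that the method would conceal a clear difference between arms. Step 4 shows otherwise, because only the limits move. A reader might also set the ±2.8 from step 3 against the ±0.39 from step 5 and conclude that most of the information is lost. Those are unlike quantities: the first is the spread of individual differences, the second the precision of a mean. The fair comparison is ±0.46 against ±0.39. This part of the objection stands.

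It can also be said that the sentence has two aims, so Bland-Altman may be meant only for the display while regression supplies the adjusted estimate, as Table 4 suggests. That reading is possible. However, the section names no regression for differentiation, and the research question in the Table 4 row concerns fidelity, quality and outcomes. The documents do not settle it. Even as a display, the plot would need pairs that do not exist. A plot of the 16 domain means in each arm would have pairs, but the text speaks of each domain and describes no such averaging.

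Finally, the protocol says that differentiation will be explored. It attaches no hypothesis test, threshold or decision rule, and the documents hold other evidence on contrast: the control's definition as a single unstructured conversation, attendance records, and the intervention-arm BECCI scores. A reader might infer that this analysis alone settles how a null result is read. It does not. These points limit the weight of the concern, but they do not make the method fit the design.

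**Conclusion.** The named method does not fit the design. No participant, deliverer or session supplies a pair, so any limits of agreement would be arbitrary, at about ±1.4 to ±2.8 points around the mean difference for an assumed standard deviation of 0.5 to 1.0. One-to-one pairing would discard about half the intervention recordings, and the promised adjusted magnitude would not come from standard limits. The differentiation section and Table 4 also name different methods.

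The conclusion about pairing rests on the design and needs no numerical assumption. The recording counts assume full attendance. The larger pair also assumes that the 76 pilot participants' sessions were recorded on the same plan, which the documents do not state. The standard deviations are assumed.

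The matter is worth correcting because the remedy is nearly free, but its reach is limited. This is a descriptive process-evaluation analysis, and the primary outcome analysis is unaffected.

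**What to change.** In the differentiation section of the protocol, replace the Bland-Altman wording with an unpaired regression of BECCI score (overall, then each domain) on arm, adjusted for site and age group. Allow for clustering by interventionist and for repeated sessions from the same participant where the number of deliverers permits. The documents do not give that number, so the form of the allowance should not be fixed to one that may not be estimable. Report the adjusted mean difference with its 95% confidence interval, and plot the scores by arm in place of the agreement plot.

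Add a sentence noting that deliverer is nested in arm, because control staff are separate. Allowing for clustering will widen the interval, but it cannot separate staff effects from arm effects.

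Make Table 4 and the differentiation section name the same method, and add a short paragraph to the SAP, which does not mention this analysis. The recordings and scoring stay as planned, so the cost is a little protocol and SAP text.
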